## **INCLUSION CRITERIA**

In order to be included in this study, patients had to meet all the following inclusion criteria:

1. Written informed consent in which the patient agrees to undergo anesthetic procedures: general, locoregional or local anesthesia (general informed consent of the ARTD Service of the HUMS for any anesthetic procedure).
2. To undergo scheduled or urgent surgery by the COT Service.

3.Have a peripheral nerve block technique performed by the Traumatology Anesthesia Unit (ATU) of the ARTD Service of the HUMS.

## **EXCLUSION CRITERIA**

The following exclusion criteria are available, comprising only those patients in whom PNB is contraindicated:

1. Patient refusal of the peripheral nerve block technique.
2. Contraindication to the performance of the peripheral nerve block technique.
3. Allergic to amide-type local anesthetics, opioids or non-steroidal anti-inflammatory drugs.

## **STATISTICS**

Data were collected in Microsoft Excel tables and IBM SPSS Version 22 for Windows [under license from the University of Zaragoza]. For all analyses a statistically significant result is assumed if  $p < 0.05$ . The statistical analysis performed includes a descriptive and inferential analysis.

A descriptive analysis of the data will be performed: the qualitative variables (age, sex, etc.) will be presented by means of the frequency distribution of the percentages of each category and the quantitative variables studied (volume of local anesthetic, concentration of local anesthetic, etc.) will be explored with the Kolmogorov-Smirnov test of conformity (goodness-of-fit test to a normal distribution). Likewise, indicators of central tendency (mean or median) and dispersion (standard deviation or percentiles) will be given.

The degree of association between variables will be examined using graphical (scatterplot) and analytical (simple correlation coefficient) methods. The interpretation of the intensity of the relationship will be performed according to the criteria established by Gerstman (2015) and Martínez-González and et al. (2014) (20,21).

Regarding the bivariate analysis or comparison between two variables (factors), the association between the factors will be investigated by means of hypothesis contrast tests. In case both variables compared are qualitative, by means of a comparison of proportions with chi-square or Fisher's exact test. If one of them is quantitative, a comparison of means will be made by means of Student's t-test, ANOVA, and if they do not follow a normal distribution, the Mann-Whitney U test or the Krustal-Wallis test. Likewise, a bivariate correlation (Pearson's correlation coefficient) will be carried out when both variables are quantitative or, if the application conditions are not met, a Spearman's correlation.

As for the multivariate analysis, to study the relationship of each variable controlling for the possible effect caused by third variables, the analysis will be completed by regression models.

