## **OBJECTIVES**

The primary objective of this study is to quantify the number and type of peripheral nerve blocks performed in the routine anesthetic practice of the Traumatology Anesthesia Unit of the Miguel Servet University Hospital. Secondary objectives are: to describe to assess the safety of peripheral nerve blocks in the routine anesthetic practice of the Traumatology Anesthesia Unit of the Miguel Servet University Hospital: number, severity and resolution of complications.

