## **DESIGN**

This is a descriptive, observational, retrospective, single-center, retrospective study of a population-based sample of all patients who have undergone orthopedic and trauma surgery and who have undergone PNB, according to standard clinical practice, in the Traumatology Anesthesia Unit of the Miguel Servet University Hospital (Zaragoza, Spain).

The source of our population sample is all patients undergoing scheduled or urgent surgery by the COT Department of the HUMS and who underwent perioperative PNB by the ARTD Department's ATU.

The registration of the cases in this study was carried out at HUMS, where the generated database is kept. The data analysis was carried out in a cross-sectional manner with a retrospective follow-up of the sample.

Patient recruitment spans from January 01, 2011 to November 30, 2019. Cases have been recruited by convenience, during the perioperative process of patients in the surgical block of HUMS, up to a total of 13759 BNPs.

Follow-up after medication administration and BNP performance lasts until the present day. It is performed by the clinical evaluation of the services responsible for patient follow-up, see the COT Service, who does not redirect possible complications encountered in the operated patients.

The anesthetic and surgical procedures have been performed, according to standard clinical practice, in the multifunctional surgical block of the HUMS.

In this work, no biological samples were obtained from a care process and no specific test was performed.

During this work, 3 figures were involved: the PI, the ICs and the anesthesiology team. The team of anesthesiologists has been in charge of performing the interventional techniques of the BNP according to the usual clinical practice and which have been collected in the BD. They were also the ones who completed the CRD after performing the PNBS. The ICs have been those who have made the BD from the CRD of all the NIBPs performed. Finally, the PI will be responsible for the processing of the DB data.

This work has been carried out within the usual care activity of the ARTD Service's TCU and this practice has been followed in all cases.

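### Age is classed as qualitative, so any test of age against complications would be a chi-square or Fisher test on age bands the plan does not state

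*Combined protocol and SAP*

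**What the plan says.** All of the relevant rules are in the STATISTICS section of the combined protocol and SAP.

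- **Type of variable.** Age and sex are the two named examples of qualitative variables: "the qualitative variables (age, sex, etc.) will be presented by means of the frequency distribution of the percentages of each category". The named quantitative examples are different: "the quantitative variables studied (volume of local anesthetic, concentration of local anesthetic, etc".
- **Scope.** "The statistical analysis performed includes a descriptive and inferential analysis", with p < 0.05 as the criterion throughout.
- **Two qualitative variables.** "In case both variables compared are qualitative, by means of a comparison of proportions with chi-square" or Fisher's exact test.
- **One quantitative variable.** "If one of them is quantitative, a comparison of means will be made by means of" a t-test or ANOVA, with Mann-Whitney or Kruskal-Wallis if the data are not normal.
- **Adjusted analysis.** "the analysis will be completed by regression models". How age is coded in these models is not stated.

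No age bands, cut-points or test for ordered categories appear anywhere. The secondary objective in OBJECTIVES is safety, described as "number, severity and resolution of complications". DESIGN says: "Patient recruitment spans from January 01, 2011 to November 30, 2019", with a total of 13,759 blocks.

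**The concern.** Age is a measured quantity, but the plan handles it as it handles sex. Three things follow.

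1. Age would be described by percentages only. Means, medians and measures of spread are attached to the quantitative variables.
2. A test of age against whether a complication occurred takes the chi-square or Fisher route. In their standard forms these tests ignore the order of the bands, so a steady rise in risk with age is harder to detect. The plan already has a better route for such a pairing, and only the classification keeps age off it.
3. The bands are left open in a retrospective study whose recruitment ended in November 2019. They can therefore be set with the outcomes already recorded, and whether an association is declared can depend on where the cuts fall.

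Age against complications is an inferred pairing. The plan lists no specific pairs, but it does plan inferential analysis, and complications are its secondary objective.

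**Working it through.** **The route through the plan's rules.** Age is qualitative as classed. Complication yes/no is qualitative. The rule for two qualitative variables gives chi-square or Fisher. If age were quantitative, the same pairing would go to a t-test or Mann-Whitney test.

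**Inputs.** The plan contains no power calculation, so there is no figure to reproduce. Only the 13,759 blocks and the 0.05 level come from the documents. The rest is assumed: two-sided tests, independent blocks, age normal with mean 60 and SD 18, z = (age − 60)/18, and complication rates of 0.5%, 1% and 2%. Expected events are 13,759 × 0.005 = 69, 13,759 × 0.01 = 138 and 13,759 × 0.02 = 275.

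**Hand check at 0.5%, OR 1.3 per SD.** For age in years the noncentrality is about N·p(1 − p)·(ln OR)² = 13,759 × 0.005 × 0.995 × 0.2624² = 4.71. Power is about Φ(√4.71 − 1.96) = Φ(0.21) = 58%. Banding keeps only the between-band share of the variance of age and spends k − 1 degrees of freedom:

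| Bands (cuts) | Share kept | Noncentrality | df | Power |
|---|---|---|---|---|
| Seven (30/40/50/60/70/80) | 0.948 | 4.47 | 6 | 30% |
| Four (40/60/80) | 0.879 | 4.14 | 3 | 37% |
| Two (65) | 0.619 | 2.92 | 1 | 40% |

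Seven bands lose power mainly through the extra degrees of freedom. Two bands lose it through discarded information.

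**Simulation of the same set-up.** Steady effect, log-odds = constant + ln(OR)·z; Pearson chi-square for the bands; 6,000 replicates for OR 1.3 and 2,000 for the other odds ratios (Monte Carlo SE at most about 0.6 and 1.1 points). Power in %:

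| Scenario | Seven | Four | Split at 65 | t-test | Mann-Whitney | Trend, seven | Trend, four |
|---|---|---|---|---|---|---|---|
| OR 1.3, 0.5% | 26.1 | 36.3 | 42.1 | 58.1 | 56.1 | 54.6 | 52.4 |
| OR 1.3, 1% | 55.1 | 67.3 | 70.1 | 87.1 | 85.5 | 84.4 | 82.7 |
| OR 1.3, 2% | 89.2 | 93.5 | 93.0 | 99.0 | 98.6 | 98.4 | 97.7 |
| OR 1.2, 0.5% | 12.8 | 18.3 | 22.5 | 31.8 | – | – | – |
| OR 1.2, 2% | 54.5 | 65.8 | 66.1 | 85.0 | – | – | – |
| OR 1.5, 0.5% | 63.1 | 73.7 | 75.6 | 91.2 | – | – | – |

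A trend test (1 df, on band number) recovers most of the loss without using age in years.

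**Dependence on the bands.** At OR 1.3 the three bandings do not all agree on significance in 34.1%, 34.1% and 11.8% of datasets at 0.5%, 1% and 2%. With no age effect (0.5%), each banding is significant in about 5% of datasets, but at least one of the three is significant in 11.0%.

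**Risk that is not steady, at 0.5%.** The last column is age in years plus a restricted cubic spline check (four knots), with the linear and the 2-df non-linear part each tested at 0.025. Power in %:

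| Shape | Seven | Four | Split at 65 | t-test | Mann-Whitney | Years plus check |
|---|---|---|---|---|---|---|
| Steady, OR 1.3 | 26.1 | 36.3 | 42.1 | 58.1 | 56.1 | 48.4 |
| Raised from age 80, OR 2.5 | 67.6 | 77.5 | 41.3 | 58.9 | 54.2 | 61.9 |
| U-shape, log-odds 0.25(z² − 1) | 73.7 | 70.7 | 7.7 | 15.3 | 9.3 | 94.1 |

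Years plus the check beats all three bandings for the steady and U-shaped risks. It does not beat seven or four bands when risk rises only from age 80.

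**The case against.** The strongest reply is about weight. The study is descriptive, no objective concerns age or risk factors, and no age-by-complication test is listed. That stands, and it confines the point to the description of age and to any association analysis that uses it.

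Age appears once, as a bracketed example in a text with other evident slips, so its listing as qualitative may be a drafting or translation error. That is possible, but the written classification still decides the test, and the same edit corrects a slip.

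The power figures rest on assumed inputs, and the large gaps lie in a middle range that nothing in the documents identifies as this study's. That also stands. At 0.1% complications and OR 1.3, power is about 9%, 10% and 12% with bands against 16% with age in years, so no method is useful. At 2% and OR 1.5 all are close to 100%. For a steady effect, these extremes narrow the gap but do not reverse it.

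Bands can also do better, as the age-80 and U-shape results show. For a U-shape, simply moving age to the t-test would be worse than seven or four bands, which is why the non-linearity check belongs in the fix. The 11% figure needs an analyst to try several bandings, and nothing in the plan says anyone will; it measures what the open choice permits. Finally, the regression may use age in years, but the plan does not say so.

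**Conclusion.** The point holds. Followed as written, the plan describes age by percentages and tests it against complications in categories it does not define, with no use of their order. This is more than missing detail, because the stated rule leads to a weaker analysis than one already in the plan.

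At OR 1.3 per SD, a steady effect and independent blocks, the loss against the t-test is 16 to 32 percentage points at 0.5% complications (58.1 − 42.1 and 58.1 − 26.1), 17 to 32 at 1% (87.1 − 70.1 and 87.1 − 55.1), and 6 to 10 at 2% (99.0 − 93.5 and 99.0 − 89.2). These sizes are illustrative, since the rate, effect, age distribution and bands are all assumed. The primary count of blocks and the count of complications are not affected. The change should be made, but the main objective does not depend on it.

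**What to change.** If age in years was recorded, which the documents do not say:

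- move age to the quantitative variables and report mean and SD, or median and interquartile range;
- test it by the plan's existing route for a quantitative variable;
- enter it in years in the regression models, with a pre-stated check for non-linearity such as a restricted cubic spline with fixed knots;
- use age bands for display only, with limits fixed before analysis.

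If only bands were recorded, state them now and name a trend test.

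The cost is one line of SAP wording and minor analysis work. The statistical price is some power if risk rises only above a high age: in the age-80 scenario, 61.9% against 67.6% with seven bands and 77.5% with four. The check also costs some power when risk is steady: 48.4% against 58.1% for the t-test alone at 0.5%.

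### Means are compared by Student's t-test and ANOVA on a normality condition alone, with no unequal-variance version; if groups differ greatly in both size and spread, the 5% level is not held.

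*Combined protocol and SAP*

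**What the plan says.** The STATISTICS section applies one threshold throughout: "For all analyses a statistically significant result is assumed if" p is below 0.05. When a quantitative variable is set against a grouping factor, the section calls for means to be compared. The tests it lists are Student's "t-test, ANOVA, and if they do not follow a normal distribution, the Mann-Whitney U test", with a Kruskal-Wallis test for several groups. The quantitative variables named are "volume of local anesthetic, concentration of local anesthetic, etc", and these "will be explored with the Kolmogorov-Smirnov test of conformity (goodness-of-fit test to a normal distribution"). No check of equal variances and no unequal-variance version of either test appears.

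The section does not say which groups will be compared on which variable. DESIGN gives the total, "up to a total of 13759 BNPs". OBJECTIVES names two factors that could define groups. Block type belongs to the primary aim, which is to "quantify the number and type of peripheral nerve blocks performed". Complications belong to the secondary safety aim: "number, severity and resolution of complications".

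**The concern.** Student's t-test and ordinary ANOVA pool the variances of the groups. When group sizes are very different, the pooled SD is in effect the SD of the large group. The uncertainty of the comparison, however, comes almost entirely from the small group. If the small group is more variable, the standard error is too small and false associations appear too often. If it is less variable, the standard error is too large and real associations are missed.

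Complication yes/no and rare block types are natural factors for these bivariate tests, and either could give a very unequal split. At stake is whether a reported link between anesthetic volume or concentration and such a factor carries the 5% error rate that the plan attaches to it.

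**Working it through.** **Inputs from the documents.** Significance level 0.05 (STATISTICS; two-sided is assumed, as the sidedness is not stated). Total 13,759 blocks (DESIGN).

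**Assumed inputs, varied below.** The share of blocks in the small group, and the ratio r = SD of small group / SD of large group. The documents give neither.

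**Formula.** Set the large-group SD to 1, with group sizes n_S (small) and n_L (large):

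- Pooled variance: sp² = [(n_S − 1)r² + (n_L − 1)] / (n_S + n_L − 2)
- Variance that Student's test uses: V_pooled = sp²(1/n_S + 1/n_L)
- True variance of the difference: V_true = r²/n_S + 1/n_L
- Large-sample type I error = 2[1 − Φ(1.96·√(V_pooled/V_true))]

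**Reproducing the plan's level.** With r = 1 the two variances are equal, and the formula returns 5.0% for every split tried, from 50% down to 0.2%.

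**Small group 1% (138 against 13,621), r = 1.5.**

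- sp² = (137 × 2.25 + 13,620)/13,757 = 1.0124
- V_pooled = 1.0124 × (1/138 + 1/13,621) = 0.007411
- V_true = 2.25/138 + 1/13,621 = 0.016378
- √(0.007411/0.016378) = 0.6727, and 1.96 × 0.6727 = 1.318
- Type I error = 18.7%

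**Same split, r = 1/1.5.** V_pooled = 0.007279 and V_true = 0.003294. The root of their ratio is 1.487, and 1.96 × 1.487 = 2.914. Type I error = 0.4%.

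**Over the assumed range (Student's t):**

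| Small group | r = 0.67 | r = 1 | r = 1.25 | r = 1.5 | r = 2 |
|---|---|---|---|---|---|
| 50% | 5.0% | 5.0% | 5.0% | 5.0% | 5.0% |
| 30% | 2.2% | 5.0% | 7.3% | 9.3% | 12.5% |
| 10% | 0.7% | 5.0% | 10.1% | 15.4% | 24.5% |
| 1% | 0.4% | 5.0% | 11.5% | 18.7% | 31.8% |
| 0.2% | 0.3% | 5.0% | 11.7% | 19.1% | 32.5% |

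**Simulation check.** With normal data and 200,000 runs per case, Student's test agreed with the formula (for example 18.8% and 0.4% for the 1% group at r = 1.5 and 0.67). Welch's t-test gave 4.9% to 5.1% in every case tried, with r from 0.67 to 2 and the small group from 0.2% to 50%.

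**ANOVA.** For four assumed groups of 10,000, 3,000, 600 and 159, ordinary ANOVA gave 20.2% when the two small groups had 1.5 times the SD of the others, 1.3% when the two large groups did, and 5.0% when SDs were equal.

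**Rank branch.** With a 1% group, normal data and equal centres, Mann-Whitney rejected in 10.8% of runs at r = 1.5, 1.3% at r = 0.67 and 5.0% at r = 1. It is less affected than Student's test, but it is not a pure test of location either.

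**Price of Welch.** With equal SDs, normal data and Student's power set at 80%, Welch's power is about 79% with 60 in the small group, 70% with 10 and 56% with 5. With the same exponential distribution in both groups, Welch's type I error is about 10% with 10 in the small group and 12% with 5, against about 4.5% for Student's test.

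**The case against.** A reader might infer that the groups will certainly be extremely unequal and that this alone moves the error rate to 19% or to zero. The documents support neither step. They give no split by complication or block type, and imbalance without a difference in SD does no harm.

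It can also be argued that, if volume has no relation at all to complications, both groups share one distribution, the SDs are equal and Student's test holds its level. That is correct. The inflated rates belong to the case of equal means with unequal spread. The plan, however, calls this branch a comparison of means, so a rejection would be read as a difference in means, and in that case the reading would be wrong.

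The t-test branch may also be used less often than it appears. Concentrations take a few fixed product values. In a simulation of volumes rounded to 5 ml (assumed SD 5 ml), Kolmogorov-Smirnov rejected normality in every run at n = 138, 1,000 and 13,621. Many comparisons could therefore go to rank tests. This narrows the reach of the point without removing it.

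Two further extensions are tempting and fail. Age is not a planned comparison of means, because STATISTICS lists it among the qualitative variables. Nor can planned confidence intervals be said to be wrong, because none are specified.

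Finally, the study is descriptive, and the safety objective is worded as description rather than as a test. This stands, and it limits how much depends on the point.

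**Conclusion.** The point holds in conditional form. The plan names only equal-variance tests for means and selects them on normality alone. Whether the 5% level fails depends on two things the documents do not give: how unequal the groups are and how far their SDs differ. Both must be present. If they are, the departure is large and can go in either direction, and it does not need an extreme split: at 10% of blocks, a 1.25-fold SD difference already doubles the error rate.

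The exposure is confined to secondary bivariate comparisons of quantitative variables such as volume and concentration. The number and type of blocks, which is the primary result, does not depend on it. This is a worthwhile and inexpensive correction to the plan, not a threat to the study's main finding.

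**What to change.** In STATISTICS, within the existing branch for comparing means, replace Student's t-test and ANOVA with Welch's t-test and Welch's ANOVA. Keep Mann-Whitney and Kruskal-Wallis for non-normal data, and add that a significant result there indicates a difference between distributions, not necessarily of location alone.

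Add a sentence for very small groups: with about 10 or fewer observations in a group, report the comparison descriptively or by rank or exact methods. Welch loses much of its power there and is unreliable for skewed data.

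The cost is a few lines of text and no new data. The loss of power is about one percentage point with 60 in the small group, but it is not negligible for groups much smaller than that, which is why the small-group sentence is needed.

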## **ETHICS**

The present study will be carried out in strict accordance with the international ethical recommendations for research in humans contained in the Declaration of Helsinki, Good Clinical Practice guidelines and following the recommendations of the AEMPS regarding post-authorization studies (22,23).

The protocol of this study will be evaluated by the AEMPS and the corresponding Autonomous Community Ethics Committee (CEICA) before proceeding with its performance and subsequent dissemination.

All patients were duly informed by the anesthesiologist in charge of the anesthetic technique to be performed and signed the general informed consent form for the performance of anesthetic techniques of the ARTD Service.

No invasive procedure added to the usual clinical practice of a BNP is performed in this research.

This work is a retrospective observational study so it does not require an insurance policy other than the insurance coverage of HUMS and SALUD for the usual clinical practice.

In this research project, there are no diagnostic tests derived from the research. No genetic analysis or any test that has relevance to the health of the patient's relatives or third parties is performed.

Likewise, no student participation is required.

Participants in this research study will not be compensated financially or with other services, nor will they be reimbursed for the expenses derived from their participation.

## **PROCESSING OF PERSONAL DATA**

The study data come from an anonymous database which does not include any patient identification data. The computer that contains this database is within the HUMS computer system with its corresponding firewall system. Access to this database is restricted to the research team (IP and IC). Each patient has been assigned a study identification code, only the research team has access to this information and is responsible for its safekeeping, all in order to protect patient confidentiality.

In accordance with the Organic Law on Data Protection (Point 5, SAS order 3470/2009), consent is not required for the collection of information in this study, given

the retrospective nature of the analysis. In any case, the exemption of consent does not negatively affect the rights and well-being of the participants as it does not alter the follow-up or the collection of information from routine practice.

This work is carried out during the usual clinical practice of the ARTD Service of the HUMS and therefore does not interfere with the care tasks of the center, nor does it increase the waiting list, nor is any medication prescribed, nor does it involve a distribution of resources that could affect the principle of justice. The patients recruited are part of the usual surgical program of the COT Service of the HUMS, so no advertisement or alternative means of patient recruitment is needed.

